3.3 Exploratory Endpoints

3.3.1

4.0 PATIENT ELIGIBILITY

In order to participate in this study a subject must meet all of the eligibility criteria outlined below.

4.1 Inclusion Criteria

4.1.1 Written informed consent obtained to participate in the study and HIPAA authorization for release of personal health information. Consent for the use of any residual material from biopsy (archival tissue) and serial blood draws will be required for enrollment.

4.1.2 Age \geq 18 years of age on day of signing informed consent

4.1.3 ECOG Performance Status of 0 or 1 (See Appendix 12.4: ECOG Performance Status)

4.1.4 Histologically confirmed squamous cell carcinoma of the head and neck, including the following subtypes: oral cavity, oropharynx, hypopharynx, larynx

4.1.5 Must have undergone gross total resection of the primary tumor with curative intent within the past 8 weeks with surgical pathology demonstrating \geq 1 of the following criteria for "intermediate" risk of recurrence:

- perineural invasion
- lymphovascular invasion
- single lymph node $>$ 3 cm or at least 2 nodes without evidence of extracapsular extension
- close margins defined as $<$ 5 mm but not frankly positive (in the case of ambiguous, controversial, or superseded margins, final clinical assessment regarding margin status will prevail)
- pathologically confirmed T3 or T4 primary tumor

4.1.6 No prior therapy to primary tumor prior to surgical resection (no induction therapy or recurrent disease).

4.1.7 Demonstrated adequate organ function as defined in the table below; all screening labs to be obtained within 14 days prior to initiating study treatment

System	Laboratory Value
Hematological*	
Hemoglobin (Hgb)	≥ 8 g/dL (acceptable to reach via transfusion)
Absolute Neutrophil Count (ANC)	≥ 1000 per mm ³
Platelets	$\geq 75,000$ per mm ³
Renal*	
Calculated creatinine clearance ¹	≥ 40 mL/min using the Cockcroft-Gault formula in Appendix 12.3
Hepatic*	
Bilirubin	$\leq 1.5 \times$ upper limit of normal (ULN)
Aspartate aminotransferase (AST)	$\leq 2.5 \times$ ULN
Alanine aminotransferase (ALT)	$\leq 2.5 \times$ ULN

1. Measured creatinine clearance (CL) >40 mL/min or Calculated creatinine clearance CL >40 mL/min by the Cockcroft-Gault formula (Cockcroft and Gault 1976) or by 24-hour urine collection for determination of creatinine clearance

***Note:** Hematology and other lab parameters that are \leq grade 2 BUT still meet criteria for study entry are allowed. Furthermore, changes in laboratory parameters during the study should not be considered adverse events unless they meet criteria for dose modification(s) of study medication outlined by the protocol and/or worsen from baseline during therapy.

4.1.8 Women of childbearing potential (WOCBP) must have a negative serum pregnancy test within 7 days prior to treatment. NOTE: Females are considered of child bearing potential unless they are surgically sterile (have undergone a hysterectomy, bilateral tubal ligation, or bilateral oophorectomy) or they are naturally postmenopausal for at least 12 consecutive months. Documentation of postmenopausal status must be provided.

4.1.9 WOCBP must be willing to abstain from heterosexual activity or to use at least 1 highly effective method of contraception from the time of informed consent until 90 days after durvalumab monotherapy treatment is discontinued (whichever is longer).

See section 5.6 of the protocol for additional details on contraception requirements for WOCBP and male participants in this trial.

4.1.10 Male patients with female partners must have had a prior vasectomy or agree to use an adequate method of contraception (i.e., double barrier method: condom plus

spermicidal agent) starting with the first dose of study therapy through 90 days after durvalumab monotherapy is discontinued.

4.1.11 Subjects must be willing and able to comply with study procedures based on the judgment of the investigator or protocol designee.

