3.2 Secondary Endpoints

- 3.2.1 Grade 3-5 acute toxicity will be evaluated according to guidelines from NCI CTCAE, v5.0 and include toxicity from the first day of treatment with immunotherapy until 30 days after completion of concurrent immunotherapy and radiation. Toxicity will include all toxicity attributed to the total study regimen (inclusive of radiation) not just to durvalumab alone.
- 3.2.2 Grade chronic 3-5 toxicity will be evaluated according to guidelines from NCI CTCAE, v5.0 and include toxicity continuing or occurring 30 days after completion of concurrent immunotherapy and radiation, and will be followed for up to 6 months.
- 3.2.3 OS will be estimated via the Kaplan-Meier method. OS is defined as the time from D1 of treatment to death from any cause.

3.2.4 Measure PD-LI expression by immunohistochemistry. Pre-treatment PD-L1 expression will be correlated with disease free survival following treatment of adjuvant durvalumab with radiotherapy

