8.0 ADVERSE EVENTS

8.1 Definitions

8.1.1 Adverse Event (AE)

An adverse event (AE) is any untoward medical occurrence (e.g., an abnormal laboratory finding, symptom, or disease temporally associated with the use of a drug) in a patient or clinical investigation subject administered a pharmaceutical product and which does not necessarily have a causal relationship with this treatment. An AE can therefore be any unfavorable and unintended sign (including an abnormal laboratory finding), symptom, or disease temporally associated with the use of a medicinal product, whether or not related to the medicinal product.

The term AE is used to include both serious and non-serious AEs.

Hospitalization for elective surgery or routine clinical procedures that are not the result of an AE (e.g., surgical insertion of central line) need not be considered AEs and should not be recorded as an AE. Disease progression should not be recorded as an AE, unless it is attributable by the investigator to the study therapy.

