8.3 Documentation of non-serious AEs or SARs

For non-serious AEs or SARs, documentation must begin from time of signature of informed consent, throughout the treatment period and including the follow-up period (90 days after the last dose of durvalumab).

During the course of the study all AEs and SAEs should be proactively followed up for each patient. Every effort should be made to obtain a resolution for all events, even if the events continue after discontinuation/study completion.

If a patient discontinues from treatment for reasons other than disease progression, and therefore continues to have tumor assessments, drug or procedure-related SAEs must be captured until the patient is considered to have confirmed PD and will have no further tumor assessments.

The investigator is responsible for following all SAEs until resolution, until the patient returns to baseline status, or until the condition has stabilized with the expectation that it will remain chronic, even if this extends beyond study participation.

Collected information should be recorded in the Case Report Forms (CRF) for that patient. Please include a description of the event, its severity or toxicity grade, onset and resolved dates (if applicable), and the relationship to the study drug. Documentation should occur at least monthly.

Adverse events will be recorded using a recognized medical term or diagnosis that accurately reflects the event (CTCAE 5.0 Meddra terms). AEs will be assessed by the investigator for severity, relationship to the investigational product, possible etiologies, and whether the event meets criteria of an SAE and therefore requires immediate notification to AstraZeneca/MedImmune Patient Safety.

The following variables will be collected for each AE:

- AE (verbatim)
- The date when the AE started and stopped
- The maximum CTCAE grade reported
- Changes in CTCAE grade
- Whether the AE is serious or not
- Investigator causality rating against the IPs (yes or no)
- Action taken with regard to IPs
- Administration of treatment for the AE
- Outcome

In addition, the following variables will be collected for SAEs:

- Date the AE met criteria for SAE
- Date the Investigator became aware of the SAE
- Seriousness criteria fulfilled

- Date of hospitalization
- Date of discharge
- Probable cause of death
- Date of death
- Whether an autopsy was performed
- Causality assessment in relation to study procedure(s)
- Causality assessment in relation to other medication

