8.4 SAEs or Serious SARs

8.4.1 Timing

After informed consent but prior to initiation of study medications, only SAEs caused by a protocol-mandated intervention will be collected (e.g. SAEs related to invasive procedures such as biopsies, medication washout).

For any other experience or condition that meets the definition of an SAE or a serious SAR, recording of the event must begin from day 1 of study treatment and continue through the 90 day follow-up period after treatment is discontinued.

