- If a patient experiences an AE that is thought to be possibly of autoimmune nature (e.g., thyroiditis, pancreatitis, hypophysitis, or diabetes insipidus), the investigator should send a blood sample for appropriate autoimmune antibody testing.

Grade 1

No dose modifications.

For Grade 1 (including those with asymptomatic TSH elevation):

- Monitor patient with appropriate endocrine function tests.
- For suspected hypophysitis/hypopituitarism, consider consultation of an endocrinologist to guide assessment of early-morning ACTH, cortisol, TSH and free T4; also consider gonadotropins, sex hormones, and prolactin levels, as well as cosyntropin stimulation test (though it may not be useful in diagnosing early secondary adrenal insufficiency).
- If TSH $< 0.5 \times \text{LLN}$, or TSH $> 2 \times \text{ULN}$, or consistently out of range in 2 subsequent measurements, include free T4 at subsequent cycles as clinically indicated and consider consultation of an endocrinologist.

Grade 2

For Grade 2 endocrinopathy other than hypothyroidism and Type 1 diabetes mellitus, hold study drug/study regimen dose until patient is clinically stable.

- If toxicity worsens, then treat as Grade 3 or Grade 4.

Study drug/study regimen can be resumed once event stabilizes and after completion of steroid taper.

Patients with endocrinopathies who may require prolonged or continued steroid

For Grade 2 (including those with symptomatic endocrinopathy):

- Consult endocrinologist to guide evaluation of endocrine function and, as indicated by suspected endocrinopathy and as clinically indicated, consider pituitary scan.
- For all patients with abnormal endocrine work up, except those with isolated hypothyroidism or Type 1 DM, and as guided by an endocrinologist, consider short-term corticosteroids (e.g., 1 to 2 mg/kg/day methylprednisolone or IV equivalent) and prompt initiation of treatment with relevant hormone replacement (e.g., hydrocortisone, sex hormones).
- Isolated hypothyroidism may be treated with replacement therapy, without study drug/study regimen interruption, and without corticosteroids.

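### The laboratory note under 4.1.7 conflicts with the adverse-event sections, so low-grade laboratory changes first seen after therapy could be left out of the any-grade chronic toxicity objective

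*Combined protocol and SAP*

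**What the plan says.** The note in 4.1.7 is keyed by asterisks to the hematological, renal and hepatic rows of the organ-function table. Its first sentence allows entry with values up to Grade 2 that still meet the table. Its second sentence moves from eligibility to adverse-event status. It covers on-study laboratory changes, which are to "not be considered adverse events unless they meet criteria for dose modification(s) of study medication outlined by the protocol and/or worsen from baseline during therapy". There are thus two ways to qualify, and only the second carries a time limit.

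Other sections are broader:

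- **8.1.1** says an adverse event can be "any unfavorable and unintended sign (including an abnormal laboratory finding), symptom, or disease temporally associated with the use of a medicinal product".
- **8.3** has non-serious events documented from consent, "throughout the treatment period and including the follow-up period (90 days after the last dose of durvalumab".
- **8.4.1** sets a similar period for serious events: "recording of the event must begin from day 1 of study treatment and continue through the 90 day follow-up period after treatment is discontinued".
- **2.2.3** asks for chronic toxicities of any grade.
- **3.2.2** defines the Grade 3-5 chronic endpoint as "toxicity continuing or occurring 30 days after completion of concurrent immunotherapy and radiation, and will be followed for up to 6 months".
- **7.1** (Time and Events Table) marks blood counts, chemistries with liver tests, and thyroid tests at end of treatment and at 3 and 6 months after therapy. It marks amylase and lipase at 3 and 6 months.

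No section says whether the 4.1.7 note or 8.1.1 takes precedence.

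**The concern.** The note covers laboratory changes over the whole study, but its worsening condition stops when therapy stops. The same Grade 1 rise in ALT or TSH is an adverse event if it appears on therapy and, under the note alone, is not one if it first appears afterwards. The acute and chronic periods are then judged by different rules.

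At stake is the completeness of low-grade chronic toxicity under 2.2.3. This is a multicenter study, and a site that follows the note would record fewer such events than a site that follows 8.1.1. The laboratory values would still be collected. What could be lost is their entry as graded adverse events, and so their place in any toxicity table.

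**Working it through.** The plan gives no figure for this point, so the check is a comparison of passages, followed by a calendar for context.

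**1. Which post-therapy laboratory changes fail both conditions of the note?** The worsening condition cannot be met after therapy. The dose-modification condition carries no time limit, so it is tested against Appendix 12.1 by value.

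| Laboratory change first seen after therapy | Appendix 12.1 | Adverse event under the note? |
|---|---|---|
| Grade 1 liver tests or creatinine | 12.1.2: no dose modification | No |
| Asymptomatic TSH elevation | 12.1.2: placed under Grade 1, no dose modification | No |
| Asymptomatic amylase or lipase up to 2 x ULN | 12.1.1: hold applies only above 2 x ULN | No |
| Abnormality judged not clinically significant | 12.1.3: no dose modification required | No |
| Grade 2 or higher immune-mediated liver tests or creatinine | 12.1.2: hold or discontinue | Yes, by value |
| Grade 2 or higher other related change | 12.1.3: hold, or discontinue at Grade 4 with judgement for laboratory values | Yes, by value, if clinically significant |

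Under 8.1.1 every row can be an adverse event. The conflict therefore lies mainly in the first four rows.

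**2. How much follow-up lies after therapy?** The inputs are three 3-week cycles and then three 4-week cycles (5.2.1). Nominal doses fall on days 1, 22, 43, 64, 92 and 120, and cycle 6 ends on day 147.

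- The 8.3 window closes on day 120 + 90 = 210. The share after the last dose is 90/210 = 43%. If therapy is taken to run to the end of cycle 6, it is (210 - 147)/210 = 30%.
- For the chronic window, 3.2.2 does not say when its six months start. Assume they start at the end of concurrent treatment, at week 6 (radiotherapy ends) or week 9 (cycle 3 ends), with the last dose at week 17. The window is then weeks 10.3-32.1 or 13.3-35.1. The share after the last dose is (32.1 - 17)/21.8 = 69% or (35.1 - 17)/21.8 = 83%.

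These are shares of calendar time, not shares of events. They show that the post-therapy period is not marginal; they do not measure what is lost.

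**3. What is one patient worth?** With 18 enrolled (9.2), 1/18 = 5.6 percentage points. The exact 95% interval is 0% to 18.5% for 0/18 and 0.1% to 27.3% for 1/18. This holds for any omission and is not an estimate of how many occur.

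**The case against.** The case for leaving the text alone has real substance.

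- **Scope.** The asterisks mark only hematological, renal and hepatic rows, so the second sentence may be meant only for abnormalities tolerated at entry. That is a fair reading, but the sentence refers to laboratory parameters in general and to the whole study.
- **Other instructions.** Footnote 6 of the Time and Events Table has changes in severity from baseline recorded throughout the trial, and 7.5 assesses any toxicity by that table. These favour 8.1.1 but do not settle which rule governs.
- **The dose-modification condition.** A reader might infer that it cannot be met once no dose remains. The note does not say so. Read as a threshold, it keeps most related changes of Grade 2 or higher.
- **Endocrine exemptions.** Appendix 12.1.2 reads "For Grade 2 endocrinopathy other than hypothyroidism and Type 1 diabetes mellitus, hold study drug/study regimen dose until patient is clinically stable", with the same exemption at Grades 3-4. A reader might infer that late hypothyroidism and Type 1 diabetes disappear. Overt cases are diseases under 8.1.1, and 8.2 lists endocrinopathies as events of special interest, so they are more than changes in a laboratory parameter.
- **The 90-day limit.** Counting three months as 91 days from day 120, the 3-month visit falls on day 211 +/- 15, at the edge of the 8.3 window. Counted from day 147, its earliest date is day 223. The 6-month visit lies outside that window whatever the note says. Part of any gap at these visits therefore comes from 8.3.
- **Analysis.** Section 9.3 tabulates only Grade 3-5 chronic toxicity, and 2.2.3 has no matching endpoint or analysis.

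These points narrow the effect. They do not remove the contradiction, because the note is a stated rule that a site could follow as written.

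**Conclusion.** The contradiction is real and its reach is limited. Under the literal reading, laboratory changes that first appear or worsen after therapy and meet no dose-modification threshold are not adverse events. These are mainly Grade 1 changes and abnormalities judged not clinically significant. They could be left out of the any-grade chronic toxicity objective at sites that follow the note.

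A reader might infer that late laboratory toxicity as a whole drops out of the safety data, or that the chronic toxicity rate is biased low. The documents support neither: 8.1.1 and 8.3 point the other way, serious events have their own 90-day recording rule in 8.4.1, and the Grade 3-5 chronic endpoint is little affected.

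The conclusion assumes that the dose-modification criteria are read by value and that the note applies beyond the asterisked rows; on the narrower scope, only the low-grade blood count, renal and hepatic changes remain. The end of therapy is undefined and could be the last dose or the end of cycle 6. No count of lost events can be derived from the documents.

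**What to change.** Delete the second sentence of the 4.1.7 note so that 8.1.1 governs. If a filter is wanted, limit the sentence to abnormalities that are present at entry and have not worsened. In that case, replace its on-therapy limit with one that runs from Day 1 through the adverse-event and chronic-toxicity follow-up.

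Deletion alone leaves the 90-day limit in 8.3, so the amendment should also say whether laboratory changes at the 6-month visit are recorded as toxicity, and when the six months in 3.2.2 begin.

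The cost is a short amendment, slightly more adverse-event entries and possibly a slightly less favourable low-grade chronic toxicity rate. No new tests are needed, and neither the sample size nor any treatment rule changes.

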4.2 Exclusion Criteria

Subjects meeting any of the following exclusion criteria will not be able to participate in this study:

4.2.1 Is currently participating in or has participated in a study of an investigational agent or an investigational device within 4 weeks of the first dose of treatment.

4.2.2 Concurrent enrollment in another clinical study, unless it is an observational (non-interventional) clinical study or during the follow-up period of an interventional study.

4.2.3 Has evidence of metastatic disease at time of diagnosis

4.2.4 Is receiving concurrent chemotherapy, investigational drug, biologic, or hormonal therapy for cancer treatment. Concurrent use of hormonal therapy for non-cancer-related conditions (e.g., hormone replacement therapy) is acceptable.

4.2.5 Treatment with any investigational drug within 28 days or 5 half-lives of Day 1 of treatment on this study, whichever is shortest.

4.2.6 Has not received any antibiotics <7 days prior to 1st dose of durvalumab. If the patient receives either IV antibiotics or >5 day treatment course (oral or IV), then the 1st durvalumab dose should not be given until 14 days of last antibiotic dose. During eligibility screening, subjects who receive any antibiotics within 30 days prior to the proposed initial infusion of durvalumab should be flagged and reviewed by the site's Principle Investigator to determine if the subject is a good candidate to receive durvalumab.

4.2.7 Known allergy or hypersensitivity to durvalumab or any of the study drug excipients.

4.2.8 Prior randomization or treatment in a previous durvalumab clinical study regardless of treatment arm assignment.

4.2.9 Current or prior use of immunosuppressive medication within 14 days before the first dose of durvalumab. The following are exceptions to this criterion:

- Intranasal, inhaled, topical steroids, or local steroid injections (e.g., intra articular injection)

- Systemic corticosteroids at physiologic doses not to exceed 10 mg/day of prednisone or its equivalent
- Steroids as premedication for hypersensitivity reactions (e.g., CT scan premedication)

4.2.10 Has received systemic steroid therapy or any other form of immunosuppressive therapy within 7 days prior to the first dose of trial treatment.

4.2.11 Active infection requiring systemic therapy including tuberculosis (clinical evaluation that includes clinical history, physical examination and radiographic findings, and TB testing in line with local practice), hepatitis B (known positive HBV surface antigen (HBsAg) result), hepatitis C, or human immunodeficiency virus (positive HIV 1/2 antibodies).

- Patients with a past or resolved HBV infection (defined as the presence of hepatitis B core antibody [anti-HBc] and absence of HBsAg) are eligible.
- Patients positive for hepatitis C (HCV) antibody are eligible only if polymerase chain reaction is negative for HCV RNA.

4.2.12 Has a known contraindication to radiation therapy, including inherited syndromes associated with hypersensitivity to ionizing radiation such as Ataxia-Telangiectasia and Nijmegen Breakage Syndrome

4.2.13 Has a history of uncontrolled liver disease (including but not limited to cirrhosis).

4.2.14 Subjects with baseline weight $\leq 40\text{kg}$ (88 lbs).

4.2.15 Female patients who are pregnant or breastfeeding (NOTE: breast milk cannot be stored for future use while the mother is being treated on study) or male or female patients of reproductive potential who are not willing to employ effective birth control from screening to 90 days after the last dose of durvalumab monotherapy.

4.2.16 History of another primary malignancy except for.

- Malignancy treated with curative intent and with no known active disease ≥ 5 years before the first dose of IP and of low potential risk for recurrence
- Adequately treated non-melanoma skin cancer or lentigo maligna without evidence of disease
- Adequately treated carcinoma *in situ* without evidence of disease

4.2.17 History of leptomeningeal carcinomatosis.

4.2.18 Has an active autoimmune disease (or inflammatory disorders) requiring systemic treatment within the past 3 months or a documented history of clinically severe autoimmune disease, or a syndrome that requires systemic steroids or immunosuppressive agents. Subjects with inflammatory disorders (including inflammatory bowel disease [e.g., colitis or Crohn's disease], diverticulitis [with the exception of diverticulosis], systemic lupus erythematosus, Sarcoidosis syndrome,

or Wegener syndrome [granulomatosis with polyangiitis, Graves' disease, rheumatoid arthritis, hypophysitis, uveitis, etc]).

The following are exceptions to this criterion:

- Subjects with vitiligo or alopecia or resolved childhood asthma/atopy
- Subjects who require intermittent use of bronchodilators or local steroid injections would not be excluded from the study.
- Subjects with hypothyroidism (e.g., following Hashimoto syndrome) stable on hormone replacement or with Sjorgen's syndrome will not be excluded from the study
- Any chronic skin condition that does not require systemic therapy
- Subjects without active HNSCC disease in the last 5 years may be included but only after consultation with the study physician
- Subjects with celiac disease controlled by diet alone

4.2.19 Has a history of non-infectious pneumonitis that required steroids or evidence of interstitial lung disease or current active, non-infectious pneumonitis.

[figure not shown]
4.2.20 Major surgical procedure (as defined by the Investigator) within 21 days prior to the first dose of investigational product (IP). Note: Local surgery of isolated lesions for palliative intent is acceptable.

4.2.21 Uncontrolled intercurrent illness, including but not limited to, ongoing or active infection, symptomatic congestive heart failure, uncontrolled hypertension, unstable angina pectoris, cardiac arrhythmia, interstitial lung disease, serious chronic gastrointestinal conditions associated with diarrhea, or psychiatric illness/social situations that would limit compliance with study requirement, substantially increase risk of incurring AEs or compromise the ability of the patient to give written informed consent.

4.2.22 Receipt of live attenuated vaccine within 30 days prior to the first dose of study drug. Note: Patients, if enrolled, should not receive live vaccine whilst receiving study treatment and up to 30 days after the last dose of study treatment.

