This protocol amendment is to revise the required antibiotic washout for subjects prior to receiving their 1st dose of durvalumab. Antibiotics are now prohibited to be given less than 7 days prior to the first dose of durvalumab. If a subject receives intravenous antibiotics or has an antibiotic treatment course of greater than 5 days (oral or IV) then the previously required longer washout period of 14 days is required. Language surrounding timing and amounts of radiation therapy was also amended to increase clarity and understanding. Additionally, this amendment is to update the Principal Investigator of the study from [name] to [name].

Editorial/Administrative

1. [name] was updated to the Principal Investigator of the study.
2. The study schema, Sections 1.6.1, 5.1, 5.2, 5.2.1, 6.1.3, 6.2, 7.3.1 and the Time and Events Table footnotes were updated to clarify the timing and fraction of radiation therapy.

Eligibility

1. Criteria 4.2.6 updated to prohibit antibiotics within less than 7 days prior to the first dose of durvalumab. If the patient receives either IV antibiotics or >5 day treatment course (oral or IV), then the 1st durvalumab dose should not be given until 14 days of last antibiotic dose.

THE ATTACHED VERSION DATED October 27, 2019 INCORPORATES THE ABOVE REVISIONS
ATTACH TO THE FRONT OF EVERY COPY OF PROTOCOL

PROTOCOL AMENDMENT # 1

AMENDMENT #1 INCORPORATES:

- Administrative Changes
- Scientific Changes
- Therapy Changes
- Eligibility Changes

Rationale for Amendment:

Due to the recent negative results for the use of tremelimumab in HNSCC, the protocol is being revised to treat subjects with durvalumab and radiation alone, without the addition of tremelimumab. This multi-center, single arm Phase II trial will evaluate the efficacy of combining radiation therapy with durvalumab as adjuvant therapy for patients with intermediate risk HNSCC. A total of 33 subjects will be accrued as depicted in the study schema. The treatment regimen will evaluate Q3 weekly durvalumab (1500 mg) with radiation in cycles 1-3, followed by single agent durvalumab (1500 mg) Q4 weekly for an additional three cycles. The study's objectives, endpoints and data analysis were updated according to the new study schema.

Administrative changes

1. Administrative editorial changes made throughout the protocol, including updates to T&E Table for consistency with Assessments language.

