10.3 Registration Procedures

Within 24 hours of subject consent, all subjects are registered in OnCore and all informed consent documentation uploaded into the OnCore Subject Console by a designee from the participating institution. Upon subject registration completion, the designee must email [contact] or call [contact] (M-F 8:30AM – 5:00PM EST) to alert the UNC LCCC Multicenter Office for initial review and assignment. Complete eligibility packets (institutionally-signed eligibility checklist and full source documentation confirming eligibility) are uploaded by the institutional designee into the OnCore Subject Console and the LCCC Multicenter Office concurrently alerted by email or phone ([contact]; [contact]) to begin review. All subjects must have final eligibility verified by the UNC Multicenter Project Manager on behalf of the UNC PI prior to starting treatment. Please allow 24 hours for source to be reviewed and notification of subject eligibility released. All subjects must maintain eligibility from the time of this notification through the beginning of treatment.

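### Exclusion 4.2.6 opens with a stray *not*: as written it bars patients free of recent antibiotics and lets through a recent short oral course

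*Combined protocol and SAP*

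**What the plan says.** The lead-in to Section 4.2 sets the rule for the list: "Subjects meeting any of the following exclusion criteria will not be able to participate in this study". Item 4.2.6 has three parts.

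- Sentence 1: "Has not received any antibiotics <7 days prior to 1st dose of durvalumab".
- Sentence 2 covers IV antibiotics or any course longer than 5 days: "the 1st durvalumab dose should not be given until 14 days of last antibiotic dose".
- Sentence 3 adds a review step: "subjects who receive any antibiotics within 30 days prior to the proposed initial infusion of durvalumab should be flagged", and the site's principal investigator then decides whether the patient is a good candidate.

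Three other places bear on how sentence 1 should read. Item 4.2.10, a parallel exclusion with a 7-day look-back, is in the affirmative: "Has received systemic steroid therapy or any other form of immunosuppressive therapy within 7 days prior to the first dose of trial treatment". The Amendment 2 rationale gives the purpose of the change: "Antibiotics are now prohibited to be given less than 7 days prior to the first dose of durvalumab". Section 10.3 requires each site to submit an "institutionally-signed eligibility checklist and full source documentation confirming eligibility", which the coordinating centre verifies before treatment starts.

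**The concern.** An exclusion should name the state that keeps a patient out. Sentence 1 of 4.2.6 names the opposite state, the absence of recent antibiotics. Applied as written, it turns away patients the trial wants and passes one kind of patient it means to keep out or delay. It also puts sentences 1 and 2 in conflict.

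What is at stake is consistent application of a current eligibility rule across the sites of a multicentre trial. Section 6.1.3 starts immunotherapy about 3 to 5 weeks after surgery, so the 30-day antibiotic look-back overlaps the postoperative period and the item is likely to be consulted. If the checklist copies the sentence, a yes/no answer to it has the wrong sign.

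**Working it through.** The plan gives no figure to reproduce. The check is one of logic.

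**Inputs.** The bar-if-met rule (4.2 lead-in); the 7-day condition (4.2.6, sentence 1); the 14-day hold after IV or >5-day courses (4.2.6, sentence 2); the intended prohibition (Amendment 2 rationale, used only as evidence of intent).

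**Rules.** Let *d* be the days from the last antibiotic dose to the first durvalumab dose, and treat no antibiotics as a very large *d*.

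- Intended sentence 1 bars when *d* < 7.
- Literal sentence 1 bars when *d* ≥ 7 or there were no antibiotics.
- Sentence 2, under both readings, blocks dosing when the course was IV or >5 days and *d* < 14.
- A patient may be dosed only if neither sentence stops it. The 30-day flag in sentence 3 leads to review, not an automatic bar, and is the same under both readings.

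| Antibiotic history | Intended: may dose? | Literal: may dose? | Differs? |
|---|---|---|---|
| None in past 30 days | Yes | No (sentence 1) | Yes |
| Oral, ≤5 days, ended 7–30 days ago | Yes | No (sentence 1) | Yes |
| Oral, ≤5 days, last dose <7 days ago | No (sentence 1) | Yes | Yes |
| IV or >5 days, ended ≥14 days ago | Yes | No (sentence 1) | Yes |
| IV or >5 days, ended 7–13 days ago | No (sentence 2) | No (sentences 1 and 2) | No |
| IV or >5 days, last dose <7 days ago | No (sentences 1 and 2) | No (sentence 2) | No |

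Four of the six answers flip: 3 wrongly barred and 1 wrongly allowed. The only history that may be dosed under the literal text is the third row, which is the one short-course history that Amendment 2 set out to prohibit.

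**The washout conflict.** After an IV or >5-day course, sentence 2 requires *d* ≥ 14 and literal sentence 1 requires *d* < 7. No value of *d* satisfies both, so such a patient can never be dosed under the literal text. With *not* removed, sentence 1 requires *d* ≥ 7, and *d* ≥ 14 satisfies both.

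**The case against.** The strongest reply is that nobody would apply the literal reading. Excluding patients because they have not taken antibiotics is absurd on its face. Sentences 2 and 3 treat exposure as the concern, and the Amendment 2 sheet, which is to be attached to every copy of the protocol, states the prohibition. The one wrongly allowed history still meets the 30-day review, the active-infection exclusions (4.2.11, and 4.2.21: "Uncontrolled intercurrent illness, including but not limited to, ongoing or active infection") and central verification. Section 5.4 permits antibiotics as supportive care during the study, so exposure alongside durvalumab is not treated as a bar to continuing. Finally, four of six is a tally of chosen histories and says nothing about how many patients are affected.

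Most of this stands as a limit on the consequences. The intent is recoverable, safeguards remain, and the tally is not a rate. The documents give no frequency of antibiotic use and no evidence of a misclassified patient. But none of it makes the sentence correct. Section 5.4 governs care on study, not entry. The Section 4.0 statement that subjects must meet all criteria does not rescue it either, because reading 4.2 as conditions to satisfy would invert every other item, metastatic disease and pregnancy included. Section 10.5.2 forbids single-subject eligibility exceptions, but reading an evident slip as intended is interpretation rather than an exception, so that rule adds no weight here.

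**Conclusion.** The concern holds. Sentence 1 of 4.2.6 has reversed polarity in the current protocol text, and the defect shows from the 4.2 lead-in and the item itself, without relying on the amendment history. The literal and intended readings disagree in 4 of the 6 histories above, and the literal text cannot be reconciled with the 14-day washout.

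This rests on applying the 4.2 lead-in as written, and on taking the intended rule to be the prohibition stated for Amendment 2. It is a drafting error in an operative rule; the choice of washout periods is not in question. The practical impact is probably small, and there is no effect on sample size, power or the analysis. It should be corrected because the rule governs who enters the trial and the correction costs almost nothing.

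**What to change.** Delete *not* from the first sentence of 4.2.6, so that it names recent antibiotic use as the excluded state, in the same form as 4.2.10. Leave the 7-day, 14-day and 30-day periods unchanged. Moving the sentence as it stands to Section 4.1 as an inclusion would also be logically correct, but it would separate the sentence from the washout and review provisions that qualify it, so deletion is better.

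Check the eligibility checklist, which is not among the documents, for the same wording and correct it if needed. The cost is one word in the next amendment plus that check.
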